6.2 Time Point Algorithms

6.2.1 Relative Day

The date of injection of Flortaucipir F 18 at imaging visit will be considered relative day 1, and the day before the injection of Flortaucipir F 18 will be relative day -1. Relative days will be calculated as follows only when the full assessment date is known (i.e., partial dates will have missing relative days):

6.2.2 Windows

Data will be reported as per the scheduled study visits. No window algorithm will be used for this study.

6.3 Screening Assessments

The baseline assessments will be the last assessment performed before the injection of Flortaucipir F 18. The screening assessments includes the assessment performed during screening period and during the Florbetapir F 18 imaging visit.

The following screening and baseline assessments will be conducted prior to the injection of Flortaucipir F 18 :

- Informed consent;
- Eligibility criteria;
- Demographics (age, birth gender, education, race, ethnicity);
- Height will be collected as part of the ¹⁸F-AV-1451 imaging visit;
- Weight will be collected at both imaging visits prior to injection;
- Medical history, concomitant medications;
- Disease history;
- ECG will be performed to assess the subject's cardiac status if not performed within the last 12 months of enrollment;
- Cognitive status interview, including MMSE;
- MRI of the brain will be performed if not performed within one year of enrollment;

- Serum pregnancy test (women of childbearing potential);
- Urine pregnancy test prior to Flortaucipir F 18 injection;
- Vital signs (pulse rate, respiratory rate, supine blood pressure) immediately prior to Flortaucipir F 18 injection; Prior to the administration of Flortaucipir F 18 injection, and after the completion of Flortaucipir F 18 imaging, prior Flortaucipir F 18 to discharge.
- Flortaucipir F 18 PET dose administration;
- Flortaucipir F 18 PET scan;
- Follow-up call to confirm subject well-being and to collect any new adverse events.

Medical history will be coded using Medical Dictionary for Regulatory Activities (MedDRA) v 21.1 or higher to the preferred term (PT) and system organ class (SOC). Prior and concomitant medications will be coded using World Health Organization (WHO) Drug Dictionary version WHODrugDDEB2201809.

Weight will be displayed in kilograms (kg), height will be displayed in centimeters (cm). Weights and heights recorded in alternate units will be converted to the units being displayed using standard conversion formulas. Body Mass Index (BMI) will be calculated as:

- $BMI \text{ (kg/m}^2\text{)} = \text{Weight (kg)}/\text{Height (m)}^2$

Each subject's age (years) will be calculated as the difference of the year of his/her informed consent date and the year of his/her birth.

The MMSE (Folstein et al., 1975) is a brief instrument used to assess cognitive function in elderly subjects. The instrument is divided into two sections:

- The first section measures orientation, memory, and attention. The maximum score for the first section is 21.
- The second section tests the ability of the subject to name objects, follow verbal and written commands, write a sentence, and copy figures. The maximum score for the second section is 9.

The range for the total MMSE score is 0 to 30, the sum of each correct answer, with higher scores indicating better cognition.

6.4 Efficacy Variables

The Flortaucipir F 18 scan will be evaluated by qualitative visual analysis and quantitatively by standard uptake value ratio (SUVr) analysis including regional SUVr.

6.4.1 Qualitative assessment for Flortaucipir F 18 PET scan and Diagnostic Performance

The *Flortaucipir F 18* PET scan image will be visually interpreted according to the following criteria:

Read Outcome		Objective Image Features
Not consistent with AD pattern (τAD+)		No increased neocortical activity, or increased neocortical activity isolated to the mesial temporal, anterolateral temporal, and/or frontal regions.
AD pattern (τAD)	τAD+	In either hemisphere, increased neocortical activity in the posterolateral temporal (PLT) or occipital region(s).
	τAD++	In either hemisphere, increased neocortical activity in the parietal/precuneus region(s), or frontal region(s) with increased uptake in the PLT, parietal, or occipital region(s).

6.4.2 Quantitative assessment for Flortaucipir F 18 PET scan (SUVr based)

For the Flortaucipir F 18 PET scan, standard uptake value ratios (SUVr) will be calculated to estimate tau globally and regionally. For global assessment, a target region derived statistically with a Multiblock Barycentric Discriminant Analysis (MUBADA) method will be used. A selected white matter region derived using a parametric estimated signal reference intensity (PERSI) method will be used as reference region for all SUVr calculations.

Voxels of interest (VOI) determined in the AAL atlas masked to exclude white matter and CSF for amygdala, anterior fusiform, posterior fusiform, anterior hippocampus, posterior hippocampus, anterior parahippocampus, posterior parahippocampus, caudate, frontal, parietal, precuneus, temporal, occipital, left frontal, right frontal, left occipital, right occipital, left parietal, right parietal, left putamen, right putamen, left temporal, and right temporal will be applied at the individual region level.

MUBADA SUVr will be the variable used in any efficacy analysis that involving flortaucipir quantitation. All regional SUVrs will be presented in listings.

6.5 Drug Concentration Measurements and Pharmacokinetic Parameters

No pharmacokinetic parameters or drug concentration measurements will be collected during this study.

6.6 Safety Assessments

6.6.1 Extent of Exposure and Compliance to Study Treatment

The extent of exposure to study drugs will be quantified for dose administered at Florbetapir F 18 PET scan visit and Flortaucipir F 18 imaging visit.

Since in this study subjects will receive a single bolus of study medication, compliance will not be calculated.

All exposure tables will display volume in millicuries (mCi)..

6.6.2 Adverse Events

All adverse events (AEs) occurring after signing the informed consent are to be recorded on the AE pages of the case report form (CRF). Any pre-existing conditions (i.e., undesirable experiences, signs or symptoms that begin prior to the Screening Visit) will be recorded on the medical history eCRF pages. The investigator's verbatim term of AEs will be mapped to SOC and PT using the MedDRA v 21.1 or higher.

Adverse Events:

An AE is any undesirable experience occurring to a subject during a clinical trial, whether or not considered related to the study drug. In this study clinically relevant abnormal finding, as well as worsening of any pre-existing condition shall be recorded as an AE. AEs that occur after administration of either drug but outside 48 hour reporting window will not be reported unless those are attributed to the study drug.

Unexpected Adverse Events:

An unexpected adverse event is an adverse event not previously reported or an adverse event that occurs with specificity, severity or frequency that is not consistent with the current Investigator's Brochure (IB).

Serious Adverse Events (SAEs):

Serious AEs (SAEs) are events that result in one of the following outcomes or constitute one of the following events:

- Death
- Initial or prolonged hospitalization
- A life-threatening experience (that is, immediate risk of dying)
- Persistent or significant disability/incapacity
- Congenital anomaly/birth defect
- Considered significant by the investigator for any other reason

Important medical events that may not result in death, be life-threatening, or require hospitalization may be considered serious adverse drug events when, based upon appropriate medical judgment, they may jeopardize the patient and may require medical or surgical intervention to prevent one of the outcomes listed in this definition.

For the summarization of AEs by seriousness, events recorded with missing seriousness will be summarized as serious, following worst case principle.

Trial Emergent Adverse Events:

Trial Emergent AEs are defined as any AEs that occur or worsen (increase in intensity and/or frequency) after the informed consent, and prior to administration of Florbetapir F 18, or between the Florbetapir F 18 injection session and Flortaucipir F 18 injection session but outside the 48 hours window following administration of Florbetapir F 18 or Flortaucipir F 18.

Treatment Emergent Adverse Events (TEAEs):

TEAEs are defined as any AEs that occur or worsen (increase in intensity and/or frequency) after administration of Flortaucipir F 18 or Florbetapir F 18 and until 48 hours post administration.

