Pre-existing conditions (i.e., undesirable experiences, signs or symptoms that begin prior to the Screening Visit) will be recorded on the medical history eCRF pages. During the study, site personnel will record any change in the condition(s) and occurrence and nature of any AEs. Signs and symptoms that are believed to be due to the pre-existing condition(s) (started prior to dose of study medication) do not have to be recorded in the AEs section of the eCRF, unless there is an increasing in frequency and severity. Additionally, signs or symptoms or changes in pre-existing conditions that occur outside the trial defined adverse event reporting period (e.g., between each imaging visit will be recorded in medical history).

An adverse event is any untoward medical occurrence associated with the use of a drug in humans, whether or not considered drug related. For the purposes of this study, untoward medical occurrences will be considered associated with the use of ¹⁸F-AV-1451, and thus be reported as adverse events, if they occur within 48 hours after administration of ¹⁸F-AV-1451. Untoward medical occurrences will be considered associated with the use of Florbetapir F 18 injection, if they occur within 48 hours after Florbetapir F 18 injection administration. Adverse events associated with the use of ¹⁸F-AV-1451 or Florbetapir F 18 injection will be recorded as treatment emergent relative to the respective drug. Adverse experiences that occur after administration of either drug but outside the 48 hour reporting window will not be reported unless the investigator believes they are attributable to the drug.

Trial-emergent adverse events are undesirable experiences, signs or symptoms that begin, or worsen in intensity or frequency, after the informed consent, and

Protocol ¹⁸F-AV-1451-A19: “¹⁸F-AV-1451 PET Imaging in Subjects with Frontotemporal Dementia”

prior to administration of study drug at the imaging visit. In order to capture possible adverse effects of trial participation, trial-emergent AEs will also be reported during the baseline imaging period but not during the 48 hour windows following the administration of ¹⁸F-AV-1451 or Florbetapir. These will be recorded on the adverse event pages.

The end of study, for the purpose of adverse event reporting, is defined as 48 hours after the last study drug administration.

Serious Adverse Event (SAE)

A SAE is an AE that results in one of the following outcomes or constitutes one of the following events:

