4 STUDY DESIGN

4.1 General Design

This is a multicenter Phase I study in subjects diagnosed with symptomatic clinical syndromes with expected FTD pathology.

Subjects followed in a referral center research cohort for FTD will be contacted to participate and must provide informed consent before starting ¹⁸F-AV-1451-A19 study procedures. Diagnosis will be determined by companion study with detailed characterization provided by enrolling physician.

Screening assessments will be conducted over several days and preferably will be performed within 60 days prior to the Flortaucipir F 18 PET imaging session. The screening assessments will include demographic information, a medical assessment for eligibility, vital signs, ECG, a brief cognitive assessment [e.g. Mini-Mental State Examination (MMSE)], and Florbetapir F 18 Positron PET imaging.

A physician will evaluate the subjects prior to administration of Florbetapir F 18 injection to determine if they are suitable to undergo the scan. Upon confirmation, the subjects will receive a single IV bolus injection of approximately 370 MBq (10 mCi) Florbetapir F 18 followed by a saline flush. A 20-minute continuous, dynamic PET brain scan will begin approximately 50 minutes following the dose administration. The screening Florbetapir F 18 PET scan is performed to assess for evidence of amyloid pathology and should be interpreted by the local reader prior to enrollment. Amyloid scans that have been obtained within 3 years of screening can be submitted for review by the local reader for enrollment criteria. If deemed interpretable, the subject would not need to complete the screening Florbetapir F 18 PET scan.

The Flortaucipir F 18 PET scan should be performed at least 16 hours apart from the Florbetapir F 18 PET scan due to the half-life of fluorine 18. Subjects who qualify for the study will come to the imaging center at a later date and will have a catheter(s) placed for IV administration of Flortaucipir F 18. Vital signs will be taken in a supine position prior to administration of Flortaucipir F 18 (within 30 minutes prior to injection) and at the completion of imaging prior to subject discharge. Upon confirmation by physician on suitability of subjects to undergo the scan, the subjects will receive a single IV bolus injection of approximately 370 MBq (10 mCi) Flortaucipir F 18 followed by a saline flush. A 30 minute dynamic image will begin approximately 75 minutes following the dose administration.

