8.10.2 Adverse Events

All AE summary tables will include only TEAEs, unless otherwise specified.

Adverse events will be summarized by SOC and PT. A subject will only be counted once per SOC and PT.

For AEs by severity grade (mild, moderate, severe), if a subject has multiple events occurring in the same SOC or same PT, then the event with the maximum intensity (i.e. severe) will be counted.

For AEs by relationship to study drug and protocol procedure will be summarized as Related vs. Not Related. If a subject has multiple events occurring in the same SOC or same PT, the event associated with the study drug will be summarized.

AEs will be summarized by descending frequency, then alphabetically by SOC and preferred term.

An overall summary of AEs will be presented and will include:

- Subjects with any Trial Emergent AEs
- Subjects with at least one TEAE
- Subjects with any severe or moderate TEAE
- Subjects with any TEAE related to Florbetapir F 18
- Subjects with any TEAE related to Flortaucipir F 18
- Subjects with any TEAE related to protocol procedure
- Subjects with any serious TEAE
- Subjects with any TEAE resulting in death
- Subjects with any TEAE leading to study discontinuation

The following summary tables will be presented by SOC and PT:

- Trial Emergent AEs
- All TEAEs
- TEAEs by PT
- TEAEs by severity
- TEAEs by relationship to Florbetapir F 18
- TEAEs by relationship to ¹⁸F-AV-1451
- TEAEs by relationship to protocol procedure
- Serious TEAEs
- TEAEs resulting in death
- TEAEs leading to study discontinuation

The following listings will be presented by subject:

- All AEs
- Serious TEAEs
- TEAEs leading to study discontinuation
- TEAEs resulting in deaths

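### The SAP ties trial-emergent adverse events to florbetapir, so pre-flortaucipir events in subjects admitted on a historical amyloid scan miss the trial-emergent tables

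*SAP*

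**What the plan says.** - **Trial-emergent events, SAP 6.6.2.** There are two limbs, joined in one sentence: "prior to administration of Florbetapir F 18, or between the Florbetapir F 18 injection session and Flortaucipir F 18 injection session". In full, the first covers events "after the informed consent, and prior to administration of Florbetapir F 18". The second covers events "between the Florbetapir F 18 injection session and Flortaucipir F 18 injection session but outside the 48 hours window" that follows either tracer.
- **Treatment-emergent events (TEAEs), SAP 6.6.2.** These occur or worsen "after administration of Flortaucipir F 18 or Florbetapir F 18 and until 48 hours post administration".
- **Historical scans, SAP 4.1, with the same allowance in Protocol 7.1.1.1.** "Amyloid scans that have been obtained within 3 years of screening can be submitted for review by the local reader for enrollment criteria". The SAP continues: "If deemed interpretable, the subject would not need to complete the screening Florbetapir F 18 PET scan".
- **Tables, SAP 8.10.2.** Summary tables hold TEAEs only, unless stated otherwise. The stated exceptions are the overview row "Subjects with any Trial Emergent AEs" and one trial-emergent table by SOC and PT. A by-subject listing covers all adverse events.
- **Denominator, SAP 8.1.** One dose of either tracer puts a subject in the Safety Population.
- **Protocol 7.7.2.** Trial-emergent events begin or worsen after consent and "prior to administration of study drug at the imaging visit". The 48-hour windows after each tracer are carved out.
- **SAP 5.2.** No changes from the protocol's planned analyses are declared.

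**The concern.** A subject admitted on a historical scan has no on-study florbetapir date. Nothing that happens to that subject can be placed before florbetapir or between the two sessions, and a TEAE cannot start before an injection. The stretch from consent to flortaucipir therefore belongs to no category. It need not be short, since SAP 4.1 prefers screening within 60 days of the flortaucipir session, and it can include study procedures such as an MRI or a blood draw.

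What is at stake is one overview row and one SOC/PT table. Once given flortaucipir, these subjects count in the denominator of both but cannot enter the numerator. Two subjects with the same pre-flortaucipir event would be tabulated differently only because of when their amyloid scan was done. Protocol 7.7.2 says that trial-emergent events are collected to pick up possible harm from taking part in the trial, and the SAP's wording drops part of that.

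**Working it through.** The plan gives no figure to reproduce here, so the check applies the definitions as rules.

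**Step 1. Rules.** Let F be the on-study florbetapir time, T the flortaucipir time and t the event time, all counted from consent.
- SAP TEAE: F ≤ t ≤ F + 48 h, or T ≤ t ≤ T + 48 h.
- SAP trial-emergent: not a TEAE, and either 0 ≤ t < F or F < t < T.
- Protocol 7.7.2 trial-emergent: not a TEAE, and 0 ≤ t < T, reading study drug at the imaging visit as flortaucipir at Visit 2.

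If F does not exist, neither part of the SAP trial-emergent rule can be true.

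**Step 2. Every hour from consent to 48 h after flortaucipir.** Assumed timing, for illustration only: T = 480 h (day 20) and, where given, F = 120 h. The hours total 480 + 48 = 528.

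| Subject | Rule | Trial-emergent | TEAE | Unclassified |
|---|---|---|---|---|
| On-study florbetapir | SAP | 480 − 48 = 432 | 48 + 48 = 96 | 0 |
| On-study florbetapir | Protocol | 432 | 96 | 0 |
| No on-study florbetapir | SAP | 0 | 48 | 480 |
| No on-study florbetapir | Protocol | 480 | 48 | 0 |

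The two documents agree for subjects given florbetapir on study. For the others, all 480 pre-flortaucipir hours are unclassified under the SAP and trial-emergent under the protocol wording. Other timings change the hour counts but not this pattern.

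**Step 3. Sensitivity to reading.** Suppose the historical scan used florbetapir (8,760 h, one year, before consent in the check) and the second limb is stretched back to that injection. Then 480 h are trial-emergent and 0 unclassified. The SAP does not say this, the word session reads as the on-study visit, and the allowance refers to amyloid scans without naming a tracer.

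**Step 4. Effect on the percentage.** Let N be the Safety Population, a the subjects counted with a trial-emergent event, and b the historical-scan subjects in N with an uncounted event before flortaucipir.
- Reported: a/N.
- Under the protocol wording: (a + b)/N.
- Shortfall: b/N, which is never negative.

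With up to 25 subjects planned, b can lie anywhere from 0 to 25. If N were 25, each such subject would be worth 1/25 = 4 percentage points. But N is not known either: subjects given florbetapir who then fail screening as amyloid-positive also enter it. With a, b and N all open, the shortfall has a direction but no computable size.

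**Step 5. The same check after the fix.** With the first limb ended at the first on-study tracer, a subject without on-study florbetapir has 480 h trial-emergent and 0 unclassified. A subject given florbetapir is unchanged at 432 h and 96 h.

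**The case against.** The strongest case on the other side has four parts.

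- **Nothing is lost from the report.** SAP 6.6.2 requires all events after consent to be recorded, and SAP 8.10.2 lists them by subject. With at most 25 subjects a reader can find them there. This stands, and it limits the point to the summary tables.
- **The consequence is small.** The study is phase I and descriptive, and the secondary objective is to expand the flortaucipir safety database. The affected events precede any study tracer in these subjects, so they do not bear on tracer safety. This also stands.
- **The protocol is not a clean comparator.** Protocol 7.7.2 also sends changes arising between imaging visits to medical history, and Protocol 7.7.4 limits reporting of SAEs before study drug to those possibly caused by a procedure. The SAP may have been trying to spell this out for the two-tracer pathway. That is fair, but it does not explain why subjects with one tracer have no rule. The protocol's trial-emergent wording does cover them.
- **The text can be read to work.** A subject never given florbetapir could be treated as always before it. The first limb would then have no end, and events after flortaucipir could be both trial-emergent and treatment-emergent. In a program, the flag could come out missing, false or accidentally true depending on how an absent date is handled. A safety table should not depend on that.

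A reader might infer a proportional shortfall: reported over true rate equal to one minus the historical-scan share. That needs the share, equal event risk in both groups and no screen failures in the denominator. The documents give no share. Historical-scan subjects skip a whole injection session, so equal risk is not shown. Florbetapir-dosed screen failures belong to the Safety Population by definition.

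**Conclusion.** The gap is real on the SAP's literal wording. For subjects with no on-study florbetapir, events between consent and flortaucipir are neither trial-emergent nor treatment-emergent, and they drop out of the trial-emergent row and table. The trial-emergent percentage is biased down whenever such an event occurs, by an amount the documents do not allow to be computed. If no subject uses a historical scan, there is no effect.

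Three stronger conclusions might be inferred, and the documents do not support them. The events do not disappear from the report, because the full listing keeps them. Not every such event is wholly untabulated, because one that worsens within 48 hours after flortaucipir is a TEAE for the worsening. And flortaucipir safety is not understated, because its TEAE counts are the same under either definition.

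The conclusion rests on reading the florbetapir session as the on-study one and the protocol's imaging visit as the flortaucipir visit. On that reading the SAP departs from the protocol without declaring it. This is a stated rule that undercounts, not merely a missing detail, so it should be corrected before the tables are programmed.

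**What to change.** Redefine trial-emergent adverse events in SAP 6.6.2 as those that start or worsen:
- after informed consent and before the first tracer administered on study (florbetapir or, if none is given, flortaucipir); or
- between the two on-study tracer sessions, outside the 48-hour windows.

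State that a historical scan does not count as an on-study session.

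In the same edit, reconcile this with the sentence in SAP 6.6.2 that withholds events after either tracer but outside 48 hours from reporting unless attributed to study drug. For subjects who do receive florbetapir, that sentence conflicts with the between-session limb. Record the outcome in SAP 5.2 if it still differs from Protocol 7.7.2.

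The cost is one redefined sentence, one reconciled sentence and one derivation rule. No new data are needed, and under the new definition the classification of subjects given florbetapir on study does not change.

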3.2 Secondary Objective

The secondary objective of this study is to expand Flortaucipir F 18 safety database.

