6.6.2.1 Classifications of Adverse Events

Severity of Adverse Events:

The severity of an AE will be graded as “Mild”, “Moderate” or “Severe”. AEs events recorded with missing intensity will be summarized as Severe, following worst case principle.

Relationship to study drug/protocol procedure:

An AE will be considered as related to Flortaucipir F 18 if they occur within 48 hours after administration of Flortaucipir F 18, and will be considered as related to Florbetapir F 18 if they occur within 48 hours after administration of Florbetapir F 18.

In addition, the investigator will assess the relatedness of an AE to protocol procedure.

Any missing relationship of an AE to study drug or protocol procedure will be considered to be related for the analysis, following worst case principle.

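### TEAE severity, seriousness, death and discontinuation are summarised only for both tracers pooled, although the safety objective concerns flortaucipir

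*SAP*

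**What the plan says.** - **Objective.** SAP 3.2: "The secondary objective of this study is to expand Flortaucipir F 18 safety database". Protocol section 2 has the same aim.
- **Protocol definition.** Protocol 7.7.2 gives each tracer its own 48-hour window and says that events associated with either one "will be recorded as treatment emergent relative to the respective drug".
- **SAP definition.** SAP 6.6.2 has a single TEAE class, covering events "after administration of Flortaucipir F 18 or Florbetapir F 18 and until 48 hours post administration".
- **Relatedness.** SAP 6.6.2.1 decides it by timing: "An AE will be considered as related to Flortaucipir F 18 if they occur within 48 hours after administration of Flortaucipir F 18". Florbetapir has a parallel rule.
- **Outputs naming a tracer.** In SAP 8.10.2 the overall summary has the row "Subjects with any TEAE related to Flortaucipir F 18" and a matching florbetapir row. The SOC/PT tables include "TEAEs by relationship to ¹⁸F-AV-1451" and "TEAEs by relationship to Florbetapir F 18".
- **Outputs not naming a tracer.** The same section lists all TEAEs, "TEAEs by severity", serious TEAEs, TEAEs resulting in death and TEAEs leading to discontinuation, with no split. SAP 7.1 puts all values into one group.
- **Counting rule.** For severity, SAP 8.10.2 keeps a subject's most intense event within a SOC or PT. Nothing restricts the rule to one tracer.

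**The concern.** Flortaucipir is the investigational agent, and its safety is what the study sets out to document. Florbetapir is a screening agent supplied under an approved NDA (Protocol 4.6). A reader of the safety tables will want to know how many subjects had a severe or serious event after flortaucipir. The planned summaries answer that only for the two tracers combined. The maximum-intensity rule adds to this: once the most intense event has been chosen across both tracers, the printed severity table can no longer be separated by tracer and would have to be rerun.

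**Working it through.** The plan states no figure to reproduce. The check compares definitions with outputs, and adds two short calculations that bear on the fix.

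**1. Is flortaucipir incidence reported?** A SAP TEAE is an event within 48 hours of either tracer. An event related to flortaucipir is one within 48 hours of flortaucipir. A TEAE related to flortaucipir is therefore a flortaucipir-window TEAE, the class that Protocol 7.7.2 describes. The one addition is that SAP 6.6.2.1 sets a missing relationship to related. The relationship row and SOC/PT table thus give incidence, under the label of relatedness.

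**2. Can flortaucipir severity be recovered from the summaries?** Take one hypothetical subject with the same preferred term after both tracers, neither event serious:

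| Summary | Case A: mild after flortaucipir, severe after florbetapir | Case B: severe after flortaucipir, mild after florbetapir |
|---|---|---|
| Any TEAE | 1 | 1 |
| Moderate or severe TEAE | 1 | 1 |
| Severity table | severe 1, mild 0 | severe 1, mild 0 |
| Related to flortaucipir | 1 | 1 |
| Related to florbetapir | 1 | 1 |

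Every planned summary is identical, yet the flortaucipir event is mild in A and severe in B. In A the mild event leaves the severity table altogether. Two subjects with the same preferred term, one after each tracer, give the same ambiguity without the maximum-intensity rule: the severity table shows one mild and one severe whichever tracer had the severe event. If a preferred term occurs only in the flortaucipir window, the severity and relationship tables read together do identify its severity. The gap therefore arises for terms seen after both tracers, and in overall rows that give no term.

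**3. Denominator for a tracer column.** The Safety Population is everyone who received either tracer (SAP 8.1). Exposure can differ. An interpretable amyloid scan within 3 years can replace the florbetapir scan (Protocol 7.1.1.1), and subjects with a positive florbetapir scan are excluded (Protocol 5.3.2) after they have received florbetapir.

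Assume 25 subjects dosed with flortaucipir (the enrolment ceiling) and s further subjects given florbetapir only. The documents do not give s. One subject with a flortaucipir event is 1/25 = 4.0% of those dosed. With the either-tracer denominator, 1/(25 + s), it is:

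- s = 0: 1/25 = 4.0%
- s = 5: 1/30 = 3.3%
- s = 10: 1/35 = 2.9%
- s = 25: 1/50 = 2.0%

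**4. Overlapping windows.** The scans must be at least 16 hours apart (Protocol 7.1.2). At that minimum the 48-hour windows overlap by about 48 − 16 = 32 hours. An event in the overlap is related to both tracers under SAP 6.6.2.1, so tracer columns need a counting rule.

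**The case against.** The strongest reply is that the protocol does not ask for this split. Protocol 8.2.2 calls for adverse events by severity, relationship and seriousness, without crossing any of these with tracer. Protocol 8.1.2 defines the safety population by either tracer, and Protocol 7.7.2 speaks of how events are recorded. Pooled tables are therefore not a departure from the protocol's analysis section. That stands. The case for the split rests on the drug-specific definition in Protocol 7.7.2 and on the flortaucipir objective.

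The second reply is that little is at stake in practice. The study is descriptive, with up to 25 subjects. SAP 8.10.2 plans listings of all adverse events, serious TEAEs, deaths and discontinuations, and SAP 7.1 adds listings of all eCRF data and derived variables. A reader could work out severity by tracer by hand. This also stands and lowers the priority, but listings do not replace a summary that addresses a stated objective.

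Three stronger readings are tempting, and the documents do not support them:

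- A reader might infer that the flortaucipir profile goes unreported, or that the protocol's drug-specific rule has disappeared. The 48-hour rule survives in SAP 6.6.2.1, and SAP 8.10.2 reports flortaucipir incidence from it.
- A reader might infer that the pooled TEAE row inflates the flortaucipir rate. Flortaucipir has its own row, so the gap between the two measures no loss. Any figure for it would also need assumed event rates and every subject receiving both tracers.
- A reader might argue that if relatedness became the investigator's judgement, as Protocol 7.7 describes, no table would show flortaucipir incidence. That depends on a change the SAP does not make, so it is not a defect of the current text.

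**Conclusion.** The point holds in a limited form. Under SAP 6.6.2, 7.1 and 8.10.2, no summary table gives severity, seriousness, death or discontinuation for flortaucipir alone, and the maximum-intensity rule as written can hide a milder flortaucipir-window event behind a more severe florbetapir-window event with the same preferred term. Flortaucipir incidence is available, but only under the label of relatedness.

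No numerical size can be given, because the documents state no event rates and no count of subjects who will receive only one tracer. The conclusion assumes that the listed tables are produced as written, as a single group. It is a minor-priority improvement to presentation, worthwhile because it is cheap and lets the tables answer the secondary objective directly.

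**What to change.** - **SAP 6.6.2:** define a TEAE relative to the respective drug, as Protocol 7.7.2 does.
- **SAP 8.10.2:** show the overall, SOC/PT, severity, serious, death and discontinuation TEAE summaries in three columns: flortaucipir window, florbetapir window and total.
- **Counting:** apply the once-per-subject and maximum-severity rules within each column.
- **Denominators:** use the subjects dosed with that tracer for each tracer column, and the Safety Population for the total.
- **Overlap:** count an event that falls in both 48-hour windows in both tracer columns, and once in the total.

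The cost is two more columns and slightly more programming. New data should not be needed, because SAP 6.6.2.1 already assigns events to a tracer by time. One point to confirm is that the eCRF holds adverse event onset times: Protocol 7.7 mentions dates and time, Protocol 7.7.3 only dates, and the CRF is not among the documents.
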